#### Overall Survival

The Kaplan-Meier estimator will be used to determine the median time to death for this patient population (along with 95% confidence intervals). The Cox proportional hazards model will be used to evaluate the effects of covariates of interest on survival.

13.3.2.5 Adverse Events

Adverse events will be reported according the CTCAE criteria.

## **13.0 DATA SAFETY MONITORING PLAN**

### 13.1 Purpose and Scope

13.1.1 The purpose of the Radiation Oncology Data and Safety Monitoring Plan is to ensure that clinical trial data is accurate and valid and to ensure the safety of trial participants.

13.1.2 The Radiation Oncology DSMC is charged with developing, implementing, and maintaining the Data and Safety Monitoring Plan. The membership consists of a Medical Director of Clinical Research as well as representation from the following groups: clinical research, nursing, regulatory, pharmacy, physicists, radiation therapists, and faculty. Ad hoc members are contacted to participate as needed

### 13.2 Procedures

13.2.1 Clinical trials are assessed for safety on a continual basis throughout the life of the trial. All SAE's and any AEs that are unexpected and possibly/likely related to study participation are reported to UTSW IRB through an electronic research system per UTSW IRB guidelines.

All clinical trials are reviewed on monthly basis for enrollment. All local SAEs are reviewed by Radiation Oncology DSMC monthly for severity and attribution. For investigator-initiated trials, all SAEs at affiliated institutions are monitored as local SAEs. The principle investigator and study coordinator will present a study treatment summary and SAEs for review. Source documents will be available for the DSMC members during the review. NCI Common Toxicity Criteria Version 4 will be used for grading and attributing adverse events.

If the SAE occurs on a multi-institutional clinical trial coordinated by the Radiation Oncology Clinical Research Office, the Clinical Research Manager or primary coordinator ensures that all participating sites are notified of the event and resulting action, within one (1) working day of the determination.

**APPENDIX I:**

STUDY PARAMETER TABLE	Pre-Treatment			Follow-Up					
	Within 5 yrs prior to registration	Within 28 days prior to registration	Within 2 wks prior to registration	Before 1 st treatment	3 mos after RT	4-6 mos after RT	9 mos after RT	12 mos after RT	24 mos after RT
Histo/cyto eval	X								
History/physical		X			X	X	X	X	X
Performance status		X			X	X	X	X	X
Serum creatinine		X							
Serum pregnancy test (if applicable)			X						
Adverse event eval					X	X	X	X	X
MRI with contrast and assessment		X			X	X	X	X	X
Head CT simulation scan				X					
HA/SIB-WBRT treatment planning				X					
Neurocognitive assessment				X	X	X	X	X	X
Fatigue assessment				X	X	X	X	X	X
Quality of Life Assessments				X	X	X	X	X	X

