#### **4.0 PRETREATMENT EVALUATIONS/MANAGEMENT**

Note: This section lists baseline evaluations needed before the initiation of protocol treatment that do not affect eligibility.

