## 6.10 Radiation Therapy Adverse Events

### 6.10.1 Definition of an Adverse Event (AE)

- 6.10.1.1 Any unfavorable and unintended sign (including an abnormal laboratory finding), symptom, or disease temporally associated with the use of a medical treatment or procedure regardless of whether it is considered related to the medical treatment or procedure (attribution of unrelated, unlikely, possible, probable, or definite).

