### 6.10.3 Expected Adverse Events

- 6.10.3.1 Acute, < 90 days from treatment start: Expected adverse events include hair loss, erythema of the scalp, head ache, nausea and vomiting, lethargy, and transient worsening of neurologic deficits. Reactions in the ear canals and on the ear should be observed and treated symptomatically.

- 6.10.3.2 Late, > 90 days from treatment start: Possible adverse events include radiation necrosis, cognitive dysfunction, visual difficulties, accelerated atherosclerosis, and radiation-induced neoplasms.

- 6.10.4 Any adverse event equivalent to CTC V.4 grade 3, 4, or 5 or which precipitates hospitalization or prolongs an existing hospitalization must be reported regardless of designation (expected or unexpected) along with the attribution. This includes all deaths that occur within 30 days after the patient was discontinued from the study regardless of attribution AND any events that occur beyond 30 days and are considered probably related to treatment.

- 6.10.5 SAE reports must be completed (the CRF plus information describing the event, the grade, and the attribution) within 48 hours of the investigator's awareness of the occurrence of the event.

- 6.10.6 Attribution of an event can be categorized as:

- Not Related
- Possibly Related
- Probably Related
- Definitely Related

- 6.10.7 Adverse events (below grade 3) do not need to be submitted immediately. Rather, they should be documented in the Adverse Events Clinical Report Form (CRF) along with a brief description of the event, grade, and attribution).

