#### 13.1.2 Secondary Endpoint

- 13.1.2.1 Cognitive function includes the HVLTR for free recall, and delayed recognition; the Controlled Word Association Test (COWAT); the Trail Making Test Parts A and B (TMT); the Medical Outcomes Scale-Cognitive Functioning Subscale (MOS); the Mini-Mental Status Examination (MMSE) after WBRT-HA/SIB for brain metastasis
- 13.1.2.2 Fatigue as measured by the Multidimensional Fatigue Inventory (MFI-20)
- 13.1.2.3 Time to radiographic progression
- 13.1.2.3 Overall survival
- 13.1.2.5 Adverse events based on CTCAE criteria

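### Adverse event evaluation is scheduled only after RT, with no scheduled pre-treatment CTCAE grade and no new-or-worse rule, so change in grade cannot be read from the scheduled data

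*Combined protocol and SAP*

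**What the plan says.** **Schedule.** In Appendix I the row "Adverse event eval" is marked at 3, 4-6, 9, 12 and 24 months after RT. All four pre-treatment columns are blank. Section 4.0 opens with the note "This section lists baseline evaluations needed before the initiation of protocol treatment that do not affect eligibility". Section 4.1 then lists neurocognitive tests, the MFI-20, scans and renal screening, but no symptom grading.

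**Endpoint and analysis.** Adverse events are a secondary objective (2.2.6) and a secondary endpoint, given in Section 13.1.2 as "Adverse events based on CTCAE criteria". The whole analysis text, Section 13.3.2.5, is "Adverse events will be reported according the CTCAE criteria".

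**Definition and recording.** Section 6.10.1.1 covers any unfavourable clinical finding that is "temporally associated with the use of a medical treatment or procedure regardless of whether it is considered related to the medical treatment or procedure". For the acute period Section 6.10.3.1 states: "Expected adverse events include hair loss, erythema of the scalp, head ache, nausea and vomiting, lethargy, and transient worsening of neurologic deficits". For events below grade 3, Section 6.10.7 says "they should be documented in the Adverse Events Clinical Report Form (CRF) along with a brief description of the event, grade, and attribution".

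**Oversight.** Section 13.2.1 of the Data Safety Monitoring Plan states: "All local SAEs are reviewed by Radiation Oncology DSMC monthly for severity and attribution".

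**The concern.** Patients enter with brain metastases, and some will already have symptoms that also appear on the list of expected radiation effects. With no control arm, nothing inside the trial shows the background level of those symptoms. The usual remedy is to grade them on the same scale before treatment and to separate events that are new or have worsened. The plan schedules no such grade and states no such rule.

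The plan does use the own-control principle elsewhere. Section 1.1 warns that cognition may already be reduced at presentation, and Section 1.5 answers this by making each patient his or her own control. Section 13.3.2.2 models MFI change from baseline. Adverse events have no counterpart to either.

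At stake is how the toxicity summary can be read. A reader could not tell from the scheduled adverse event data whether a grade 1 or 2 headache at follow-up was there at the start, had worsened, or was new.

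**Working it through.** The plan states no figure on this point, so there is nothing to reproduce. The check sets the sections side by side and then counts what a fix can still reach.

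**1. Is the blank baseline cell unusual within Appendix I?** Seven rows are marked at follow-up: history/physical, performance status, adverse event evaluation, MRI, neurocognitive, fatigue and quality of life. Six of the seven also have a pre-treatment mark. Adverse event evaluation is the only one without.

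**2. Which listed symptoms are exposed?**

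| Symptom in 6.10.3.1 | Is worsening required in the text? | Baseline information elsewhere |
|---|---|---|
| Headache | No | FACT-BR item An10 |
| Nausea, vomiting | No | FACT-BR item GP2 (nausea); no item for vomiting |
| Lethargy | No | MFI-20, modelled as change (13.3.2.2); FACT-BR item GP1 |
| Neurologic deficits | Yes | FACT-BR items Br19-Br21; no scheduled CTCAE starting grade |

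Headache and nausea/vomiting are the clear cases. Lethargy is partly covered. For neurologic deficits the text asks for worsening, but no CTCAE grade is scheduled to measure it from. A baseline history/physical is also required (3.1.4). None of these sources is stated to be on the CTCAE scale, and none is linked to Section 13.3.2.5.

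**3. When is the first scheduled evaluation?** RT lasts 2 to 2.5 weeks (6.1.1.1), or 14 to 17.5 days, and three months is about 91 days.
- 14 + 91 = day 105
- 17.5 + 91 = day 108.5

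That is 15 to 18.5 days after the 90-day acute window in 6.10.3.1 closes.

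**4. How many patients could still get a prospective grade?** Section 13.2 (Sample Size) gives 50 registered patients, of whom 32 are already in the internal pilot.
- Remaining: 50 - 32 = 18, and 18/50 = 36%
- Abstracted only: 32/50 = 64%
- Remaining patients alive at 3 months under the plan's 60% death rate: 18 x 0.40 = 7.2
- If the pilot's HVLT-R completion of 9/32 = 28.1% is assumed to apply to adverse event visits: 18 x 0.281 = 5.1

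The Schema gives a sample size of 102 instead of 50. On that number the abstracted share would be 32/102 = 31%.

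**The case against.** The case on the other side is substantial.

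- **A baseline grade may exist.** A reader might infer that no pre-treatment grade is collected at all. The documents do not support that, because the Initial Evaluation Form is listed in Section 12.0 and its content is not shown. What is established is that no grade is *scheduled* in Appendix I or Section 4.1.
- **Section 4.1 is not exhaustive.** It is limited to items that do not affect eligibility, and it omits the baseline FACT-BR and EQ-5D that Section 11.5.1.1 and Appendix I require. Its silence is weak evidence, so the Appendix I row carries the point.
- **The definition and attribution already help.** On a natural reading, a symptom that predates treatment and has not changed is not temporally associated with it. Attribution is recorded for events of every grade. A reader might infer that unchanged symptoms will be counted and toxicity overstated; the documents do not show this. They show only that no explicit rule prevents it: the definition keeps events whatever their relatedness, and Section 13.3.2.5 does not use attribution.
- **The DSMC reviews attribution monthly.** It does so for SAEs, which leaves most grade 1-2 headache or nausea outside that review.
- **The route is narrow.** At the first scheduled evaluation an unchanged baseline symptom would have to have lasted more than three months. Headache and nausea are named only among acute events. The lack of a scheduled evaluation inside the acute window is arguably the larger gap, and a baseline grade does not close it.

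These points limit how far the concern reaches. They do not supply a common-scale starting grade or a rule for using one.

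**Conclusion.** The point holds as a low-priority improvement. For symptoms that the disease can also cause, change in CTCAE grade cannot be read from the scheduled adverse event data, and telling disease from treatment rests on the investigator's attribution.

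The size is unknown. The documents give no baseline symptom prevalence, so no inflated rate should be inferred.

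A reader might also take this as a threat to the trial's conclusion or its safety monitoring. The documents do not support that. The primary HVLT-R test, its sample size and its error rate do not use adverse events, no hypothesis test or stopping threshold depends on them, and SAE review continues as written. Only descriptive reporting is affected, and Section 13.3.2.5 does not fix its format.

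The conclusion assumes that the unseen Initial Evaluation Form does not already hold CTCAE grades. If it does, the collection step below is unnecessary and only the reporting rule is missing. The patient counts assume that 32 are enrolled and 50 is the target.

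**What to change.** 1. Mark adverse event evaluation in the Before 1st treatment column of Appendix I. Record there the CTCAE v4 grade of the Section 6.10.3 symptoms for all remaining patients. Neurocognitive, fatigue and quality-of-life assessments are already done at that point, so no visit is added.
2. For patients already enrolled, abstract the grade from the baseline history/physical and flag it as abstracted. The baseline FACT-BR items can support this, but they are not CTCAE grades.
3. Then state in Section 13.3.2.5 that events that are new or of higher grade than baseline will be reported, by attribution, beside all events.

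Step 3 depends on a baseline grade from step 1 or 2 and cannot be adopted alone. Keeping the all-events report means no information is lost.

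The cost is a short added CRF section, one sentence in Section 13.3.2.5 and chart abstraction for 32 patients. The downside is that those 32 of 50 (64%) get a less exact, retrospective grade, and only about 5 to 7 patients would reach the first scheduled evaluation with a prospective one.

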**Appendix II:**

**Follow-up Radiographic Assessment**

Date of MRI:

Patient Name:

Treated metastases

Lesion Number	Side (L,R,ML) & Location	d AP (cm) (Ant-Pos)	d ML (cm) (Med-Lat)	d SI (cm) (Sup-Inf)	Bidimensional product 
First set of treated metastases					
1					
2					
3					
4					
5					
6					
7					
8					
9					

 Bidimensional product = largest dimension x second-largest dimension

New Brain Metastases outside the hippocampus? (yes/no)

Number

New Brain Metastases within the hippocampus? (yes/no)

Number

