##### 11.6.1 Criteria for CNS Progression

###### 11.6.1.1 Assessment

The the bidimensional product for each of the 1-3 largest brain metastases identified at baseline will be recorded. The bidimensional product is defined as the largest dimension multiplied by the second largest dimension that is perpendicular to it (the largest dimension). This value will be recorded on the baseline form and every subsequent follow-up form. The appearance (yes/no and number) of any new brain metastases within the whole brain minus the hippocampal region will be recorded on all follow-up forms. The appearance (yes/no and number) of any new brain metastases within the hippocampal avoidance region (the hippocampus plus 5 mm) will be recorded on all follow-up forms.

Recurrences will be categorized as either within the hippocampal avoidance region or elsewhere within the brain. Therefore, there will be 3 kinds of local recurrences

reported: a) in the brain, b) in the hippocampal avoidance region, and c) elsewhere in the brain.

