11.6.1.2 Definition of CNS Progression

CNS progression will be defined as a defined increase (see below) in perpendicular bidimensional tumor area for any of the tracked brain metastases, or the appearance of any new brain metastasis on a follow-up MRI.

For lesions < 1cm in maximum diameter, a minimum increase of 50% of perpendicular bi-dimensional treatment area will be necessary to score as progression. This caveat is included to account for potential variability in measurement, which will be most susceptible to proportionate errors at smaller sizes.

For lesions > 1cm in maximum diameter, the definition will use a 25% rule for change.

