##### 13.3.2.3 Radiographic Progression

The Kaplan-Meier estimator will be used to determine the median time to radiographic progression for this patient population (along with 95% confidence intervals). The Cox proportional hazards regression model will be used to evaluate the effects of covariates of interest on time to radiographic progression.

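### Appendix II records fixed-axis extents and no maximum diameter, so for elongated oblique lesions it may not yield the perpendicular area and size class on which Section 11.6.1 bases progression

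*Combined protocol and SAP*

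**What the plan says.** Section 11.6.1.1 has the bidimensional product of each of the one to three largest baseline metastases recorded, and defines it as "the largest dimension multiplied by the second largest dimension that is perpendicular to it". It adds: "This value will be recorded on the baseline form and every subsequent follow-up form".

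Section 11.6.1.2 calls progression on a rise in perpendicular bidimensional area of any tracked lesion, or on any new metastasis. Below 1 cm maximum diameter, "a minimum increase of 50% of perpendicular bi-dimensional treatment area will be necessary to score as progression". Above that, "For lesions > 1cm in maximum diameter, the definition will use a 25% rule for change".

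Appendix II, the follow-up form, has columns for three extents (anterior-posterior, medial-lateral, superior-inferior) and one for the product. Its footnote reads "Bidimensional product = largest dimension x second-largest dimension". It has no column for the longest diameter or for the diameter perpendicular to it. The baseline form is not in the document.

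The result feeds Section 13.3.2.3: "The Kaplan-Meier estimator will be used to determine the median time to radiographic progression for this patient population".

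**The concern.** The progression rule needs two things from each tracked lesion: a perpendicular area, and a maximum diameter to choose the threshold. The only lengths the form collects are extents along fixed anatomical axes. For a lesion lying oblique to those axes, the largest extent is not its longest diameter, and the product of two extents is not the product of its own perpendicular diameters.

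Using the same form at every visit does not always remove the difference, because the two measures can change by different percentages. Progression follows from any one tracked lesion, so a single call near the threshold can set or delay a patient's event date.

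**Working it through.** The plan states no figure to reproduce, so this is a geometric check. The 25% and 50% thresholds and the 1 cm cut come from Section 11.6.1.2, and the two product definitions from Section 11.6.1.1 and Appendix II. Lesion shape, tilt and growth pattern are my assumptions; the document gives none of them.

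**Formulas.** Take an ellipse with diameters a (long) and b (short), tilted by t in one plane, with the third direction small enough not to enter either product.

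- Own-diameter product: a x b.
- Axis extents: E1 = sqrt(a²cos²t + b²sin²t) and E2 = sqrt(a²sin²t + b²cos²t).
- Form product: E1 x E2. At 45 degrees this is (a² + b²)/2.

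**Baseline 2.0 x 1.0 cm.** The own-diameter product is 2.00. The form product at 45 degrees is (4 + 1)/2 = 2.50.

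| Growth to (cm) | Own diameters | Form, 45 degrees | Form, smaller tilt |
|---|---|---|---|
| 2.3 x 1.0 | 2.30/2.00 = +15% | 3.145/2.50 = +25.8% | +20.8% at 20 degrees |
| 2.0 x 1.25 | 2.50/2.00 = +25% | 2.781/2.50 = +11.3% | +18.0% at 20 degrees |
| 2.4 x 1.0 | 2.40/2.00 = +20% | 3.38/2.50 = +35.2% | +32.7% at 30 degrees |
| 2.0 x 1.3 | 2.60/2.00 = +30% | 2.845/2.50 = +13.8% | +16.8% at 30 degrees |

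At 45 degrees, short-axis growth reaches +25% on the form only at 2.0 x 1.5 cm (3.125/2.50), which is +50% by the lesion's own diameters.

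**Where there is no difference.** If a = b, both extents equal a. If t = 0, E1 = a and E2 = b, whatever the growth. If both diameters grow by the same factor s at fixed tilt, both products grow by s²; for example, s = 1.1 gives +21% under each.

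**Change of tilt or of method.** An unchanged 2.0 x 1.0 cm lesion that moves from 0 to 10 degrees of tilt reads +3.2% on the form. The same unchanged lesion at 45 degrees, measured by its own diameters at baseline (2.00) and by extents at follow-up (2.50), reads +25%.

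**Choice of rule.** A 1.1 x 0.6 cm lesion at 45 degrees has both in-plane extents equal to sqrt((1.21 + 0.36)/2) = 0.89 cm. Its maximum diameter puts it under the 25% rule; the form's lengths would put it under the 50% rule.

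**Other orientations.** I drew 20,000 random three-dimensional orientations and multiplied the two largest extents. Two growth patterns were tested: long-axis growth of +20% by own diameters, and growth of both short axes giving +30%.

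- 2 x 1 x 1 cm: the first reads at least 25% on the form in 88% of orientations; the second reads below 25% in 87%.
- 1.5 x 1 x 1 cm: the same figures are 67% and 40%.

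These are shares of orientations for chosen shapes and growth patterns. They do not estimate how many calls would change in this trial.

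**The case against.** The strongest reply is that nothing conflicts. Section 11.6.1.1 speaks of dimensions, not diameters. The three axes on the form are mutually perpendicular, so the two largest extents satisfy its wording literally. This stands: a reader might infer a plain contradiction between the section and the form, and the wording does not establish one. What remains is an ambiguity. The perpendicularity condition would be redundant if only the three axes were meant, and Section 11.6.1.2 asks for a maximum diameter that the form does not hold.

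Second, the footnote does not say that the product must come from the three extent columns. An assessor could enter the Section 11.6.1.1 value directly, and Section 12.0 has the progression scan and report submitted, from which a diameter could be read. This also stands. The form permits the axis-based product; the document does not show that it was used.

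Third, the 45-degree examples are chosen. At 20 degrees the 2.3 x 1.0 cm example reads +20.8%, below 25%, so that false call disappears. The missed call remains, at +18.0% against +25% if the rule is read as at least 25%.

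Fourth, a reader might infer that relative change survives only when a lesion grows equally in all directions. That is too strong. Aligned lesions are unaffected by any growth pattern, and for oblique ones the condition is proportional growth at fixed tilt.

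**Conclusion.** The point holds as a measurement definition to be reconciled. As written, the form does not capture the maximum diameter that selects the threshold. If the largest dimension means the lesion's own longest diameter, the form also gives a different percent change for elongated oblique lesions that grow non-proportionally, change tilt, or are measured differently at baseline. At a 2:1 ratio and 45 degrees the gap is about 11 to 16 percentage points in either direction, enough to cross the 25% line. It shrinks with less tilt or elongation and is nil in the cases listed above.

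Three stronger conclusions do not follow:

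- **That median time to progression is biased in a known direction.** Errors run both ways, and the document gives no lesion shapes, tilts or growth patterns from which to estimate a net effect.
- **That local control is also distorted.** The thresholds define CNS progression, and Section 13 gives no local-control analysis that uses them.
- **That the trial's main conclusion is at risk.** The primary delayed-recall endpoint and its sample size do not use the product. New metastases count as progression whatever the product.

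The effect is confined to growth-based calls in one secondary endpoint.

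**What to change.** State one measurement definition and use it in Sections 11.6.1.1 and 11.6.1.2 and on both the baseline and follow-up forms. Specifically:

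- Give Appendix II, and the baseline form to match, columns for the largest diameter and the largest diameter perpendicular to it.
- Compute the product from those two columns.
- Use the recorded largest diameter to choose between the existing 25% and 50% rules.

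For patients already enrolled, first establish how the recorded products were obtained. Re-measure stored scans only for tracked lesions whose product came from axis extents, or whose baseline and follow-up methods differ. Blanket re-measurement is not warranted without evidence of either.

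The cost is a form revision and limited reading time, with no new imaging. For the 32 pilot patients in Section 13.2, at up to three tracked lesions each, the ceiling is 32 x 3 = 96 lesions, each read on the scans concerned.
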